#### **6.4.2 Physical Examination**

Physical examinations recorded at screening, baseline, all treatment visits, and all follow-up visits, will include examination of the following body systems: Dermatologic, Immunological/Allergies (other than to medication), HEENT, Endocrine, Respiratory, Cardiovascular, Genitourinary/Reproductive, Musculoskeletal, Neurological,

---

Psychological/Psychiatric and Other. All findings for 'Other' systems for the same subject at the same visit will be grouped together for summary and labelled as "Other".

The number and percentage of subjects with results recorded as normal, abnormal not clinically significant, abnormal clinically significant, related to TTP and not done will be summarised by treatment and visit for each body system.

### 6.4.3 Vital Signs

Vital signs, performed at every visit, will include temperature, supine heart rate and supine diastolic and systolic blood pressures. Supine recordings will be made after the subject has been recumbent for 5 minutes. The CRF allows a selection of units in which to record temperature, but measurements will be converted to consistent units for summarisation. Temperature will be summarised in degrees Celsius. See [Section 3](#) for unit conversion.

Weight, height and BMI will also be summarised within the Vital Signs table. The CRF allows a selection of units in which to record these parameters, but measurements will be converted to consistent units for summarisation. Weight will be summarised in kg, height will be summarised in cm. See [Section 3](#) for unit conversions.

The absolute values of temperature, supine heart rate, supine systolic and diastolic blood pressures, weight (screening and baseline only), BMI (screening and baseline only) and height (screening only) will be summarised at each visit by treatment using the summary statistics for continuous variables. Change from baseline values will also be presented for post baseline visits.

### 6.4.4 Electrocardiogram

A 12-lead ECG will be recorded after at least 5 minutes in the supine position at baseline (15minutes – 6 hours prior to PE and study drug), day 1 (4 – 6 hours post study drug), day 4 (4 – 6 hours post study drug), pre-discharge, weekly (+/- 2 days) post-discharge (during continued study drug administration), 1 month (+/- 3 days) follow-up, 2 month (+/- 7 days) follow-up, 3 month (+/- 15 days) follow-up, 6 (+/- 15 days) month follow-up, 12 (+/- 15 days) month follow-up and at any AE occurrence or other unscheduled visits.

---

If ECG is abnormal at baseline, additional ECG measurements will be taken daily during hospitalisation.

The absolute values of heart rate, PR, QRS, QT, QTc (Bazett) and RR will be summarised at baseline and each post-drug visit by treatment using the summary statistics for continuous variables. Change from baseline values will also be presented for post baseline visits.

The number and percentage of the subjects with Normal / Abnormal Not Clinically Significant / Abnormal Clinically Significant categorical ECG results will be summarised by treatment and visit.

The shifts in Normal / Abnormal Not Clinically Significant / Abnormal Clinically Significant results from baseline to all subsequent ECG readings will also be summarised by treatment and visit.

#### **6.4.5 Laboratory Parameters**

Normal ranges as provided by Ablynx will be presented in the data listings. Each parameter outside the normal range will be assigned as H (high) or L (low) on the laboratory sheet. The Investigator has to interpret each “outside the normal range” value as n.c.s. (not clinically significant) or c.s. (clinically significant). In the latter case the Investigator has to give a comment and the deviation is judged as an AE or SAE as appropriate. If the units are written into the CRF they will be converted to the preferred (standard, SI) units as specified in the CRF for each parameter.

The following laboratory tests are to be performed at the times indicated in the Schedule of Assessments ([Appendix I](#)):

- Hematology: hemoglobin, hematocrit, mean corpuscular hemoglobin (MCH), mean corpuscular haemoglobin (MCHC), mean corpuscular volume (MCV), optical platelet count (if not available, can be replaced by measurement based upon impedance),

---

immature platelet fraction (can be omitted), RBC, reticulocytes, WBC (neutrophils, lymphocytes, monocytes, basophils, eosinophils)

- Coagulation: fibrinogen, aPTT, PT, INR, vWF:Ag, factor VIII chromogenic or alternative method (e.g. one stage clot test), lupus anticoagulant, anticardiolipin antibodies (IgG, GPL; IgM, MPL; IgA, APL)
- Chemistry: glucose, haptoglobin, GGT, total bilirubin, alkaline phosphatase, AST, ALT, LDH, hCG (for women, only if urine pregnancy test is not feasible or inconclusive), c-reactive protein (CRP), rheumatoid factor, antinuclear antibody, iron, ferritin, transferrin, creatinine, urea (BUN), uric acid, protein, albumin, sodium, potassium, calcium, magnesium, chloride
- Urinalysis: pH, specific gravity, protein, glucose, ketones, bilirubin, blood, nitrite, urobilinogen, leukocytes, RBC, RBC casts, WBC, WBC casts
- Pregnancy test (urine or blood): females only at baseline
- Blood Typing (ABO), Rhesus factor in Blood (Rh), Direct Antiglobulin Test (DAT)

Continuous laboratory variables (hematology, coagulation, and chemistry parameters) will be summarised as actual result, change from baseline and percentage change from baseline for all available visits by treatment group. Urinalysis is collected at screening only and selected urinalysis parameters will be summarised for the actual result only.

Summary tables presenting the shift in result (low, normal, high) from baseline to Day 1 after last PE and from baseline to last day of treatment phase will be presented for each laboratory parameter for hematology, coagulation and chemistry parameters.

The number and percentage of subjects with abnormal laboratory results will be presented by treatment and visit for all tests and visits with at least one abnormal result. In the event that a subject has multiple abnormal values for the same test at the same visit, they will be counted only once in the summary.

---

The number and percentage of subjects within each blood typing, Rh and DAT status will be presented by treatment. This summary is provided as part of the background characteristics described in [Section 6.2.3](#).

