Inhibition of the biomarker RICO was observed in all doses groups ranging from 70% inhibition in the 2 mg dosing group to approximately 90% inhibition in the other SD groups. Reversal towards basal levels took place after approximately 72 h post dosing. A rapid and sustained inhibition of approximately 90% was observed after dosing in both MD groups. Values returned to basal levels at day 15 and day 22 after 7 days and 14 days MD respectively. In all dose groups of the SD part of the study complete RICO inhibition (defined as values < 20%) was observed from 4-18 h (2 mg), 12-18 h (4 mg), 4-24 h (8 mg), 4-36 h (10 mg) and 4-48 h (16mg) after dosing. In both groups of the MD part of the study RICO was completely inhibited from 2-168 h after dosing, i.e. from day 1-8 (7 day) and from 2-360 h after dosing, i.e. day 1-16 (14 day). A summary of the main PD findings is provided in Table 6.

Table 6: Summary of main PD results (number (%) of subjects with event).

Dose level	Subjects (n)	RICO < 20%		vWF < 50%	FVIII < 50%	
		Subjects (%)	Start (h)*			Stop (h)*
SD						
2 mg	3	2 (67)	2-4	12-18	3 (100)	0 (0)
4 mg	3	2 (67)	4-6	18-36	1 (33)	1 (33)
8 mg	3	3 (100)	2-4	18-48	3 (100)	3 (100)
16 mg	3	3 (100)	1-4	48	0 (0)	2 (67)
10 mg	3	3 (100)	2-6	24-36	3 (100)	3 (100)
Placebo	5	0 (0)	NA	NA	0 (0)	0 (0)
MD						
10 mg (7d)	6	6 (100)	2-4	168-192	5 (83)	3 (50)
Placebo (7d)	2	0 (0)	NA	NA	0 (0)	0 (0)
10 mg (14d)	6	6 (100)	2-4	336-360	5 (83)	5 (83)
Placebo (14d)	2	0 (0)	NA	NA	0 (0)	0 (0)

* Time relative to first administration

NA: not applicable

Safety

Overall the study drug ALX-0081 was well tolerated and there was no difference in the number of subjects with AEs and their respective severity between the ALX-0081 treatment groups and placebo. In all doses of the SD part of the study the related AEs were low and in all verum categories no more than 1 subject reported 1 related AE. In the MD 7 days part of the study, a total of 5/6 subjects (83%) reported 13 related AEs in the verum group compared to 2/2 subjects (100%) reporting 2 related AEs in the placebo group. In the MD 14 days part of the study a total of 6/6 subjects (100%) reported 46 related AEs in the verum group compared to 1/2 subjects (50%) reporting 1 related AE in the placebo group. A dose

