In the 13-week and 26-week RD toxicity studies in cynomolgus monkey, anti-FVIII antibodies (AFA) were detected in 4 male animals with no associated clinical signs, and in one animal with associated haemolytic anaemia, signs of inflammation and extremely low FVIII:C activity. More details are included in Section 4.3 of the Investigator's Brochure.

A good understanding of the biology of vWF and the clinical presentation of patients with deficiency of vWF helps to understand the observations seen in the conducted preclinical and clinical studies and to assess the risk for bleeding appropriately. It is well known that most patients suffering from a deficiency of vWF (vWD) have mild-to-moderate quantitative deficiencies of vWF and FVIII, which are co-ordinately reduced to 5 to 30 percent of normal plasma levels (5 to 30 IU/dL).¹² This reduction is not associated with spontaneous bleeding but with bleeding after surgery (which is typical of coagulopathies) and mucosal tract haemorrhages such as epistaxis and menorrhagia (which are typical of thrombocytopathies). It should be taken into account that these patients have a chronic, i.e. life-long, impairment of vWF and their vWF levels always stay far below 30 IU/dL. These patients don't receive regular prophylaxis, because their bleeding tendency is less severe. Only in patients with chronic and complete absence of vWF or levels below 5-10 IU/dL is a prophylaxis with vWF and FVIII indicated.

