In healthy subjects, s.c. administration of ALX-0081 as a SD or administered as daily injection for up to 14 days was well tolerated and no difference could be detected regarding the number of subjects with AEs and their severity. All injection and puncture site reactions were of mild intensity and were classified as clinically not relevant. S.c. administration of ALX-0081 as a SD or administered as daily injection for up to 14 days resulted in a fast and reversible decrease of FVIII and vWF. The average decrease of vWF levels ranged from approximately 50% decrease in low dose groups to 70% decrease, compared to pre-dose level, in the high dose groups. For FVIII, a rapid average decrease can be found in all doses groups ranging from 30%, compared to pre-dose level, in the 2 mg dosing group to 50-65% in the other SD groups. Reversal takes place after approximately 72 h after dosing. A sustained decrease of approximately 50% can be found after dosing in both MD groups. Levels are back to basal levels after approximately 48 h post dosing in the MD groups. None of the observed decreases in FVIII were recorded as abnormal/clinically significant PD assessments or as AEs.

In summary, in all healthy subjects and patients with stable angina, the treatment with ALX-0081 resulted in a rapid and reversible reduction of vWF and FVIII levels, but this reduction never reached the levels indicating spontaneous bleeding for patients with mild or

more severe forms of vWD. It is therefore expected that the further administration of ALX-0081 does not result in a clinically significant reduction of vWF and FVIII mandating prophylaxis or treatment for an imminent bleeding risk. Of note, vWF as antidote is readily available in the respective treatment institutions and would immediately antagonise the activity of ALX-0081 and Preclinical studies have demonstrated that vWF concentrates can indeed antagonise the activity of ALX-0081.

Immunogenicity

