2.6 Rationale for Dose Selection

The initial i.v. administration of investigational drug prior to the first PE on study is justified based upon a Phase I study in healthy volunteers as well as a Phase Ib trial in ACS patients. In both studies, an immediate PD effect was observed, namely RIPA \leq 10% in healthy volunteers and RICO \leq 20% in ACS patients (see section 2.4). It is believed that all active ULvWF present in the blood that has not yet aggregated platelets can be inhibited from further platelet aggregation by saturating it with the immediate i.v. injection of 10 mg anti-vWF Nanobody. This would allow for predicted protection by the investigational product against further platelet aggregation until the time of start of PE therapy.

The further administrations of the investigational drug will be performed by the s.c. injection route. The proposed s.c. dosing regimen of the ALX-0081 was investigated in a Phase I study with healthy volunteers. The daily dosing of ALX-0081 10 mg as s.c. injection resulted in a complete and sustainable inhibition of the biomarker RICO indicating the complete suppression of vWF-mediated platelet aggregation. PK modeling of these subjects with normal vWF pre-treatment levels demonstrated that the required occupancy of the target vWF resulting in maximum PD effect (i.e. RICO \leq 20%) is seen for a wide range of ALX-0081 plasma concentrations, i.e. between 100-500 ng/mL for 7 treatment days and between 100-350 ng/mL for 14 treatment days. This implies that the maximum pharmacological effect can already be achieved at relative low plasma levels of ALX-0081. Taking into consideration that vWF plasma concentrations in patients with signs and symptoms of TTP can be considerably higher than in healthy volunteers, these data suggest that the proposed doses allow for full target occupancy and subsequent complete inhibition of the biomarker in patients with vWF levels within the range of 1 to 3 fold above the previously studied levels in healthy subjects and patients suffering from ACS. This range of target occupancy (i.e. saturation of plasma vWF) lies within the reported levels of plasma vWF for patients undergoing PE as treatment for TTP.^{25,26}

The dosing scheme allows for a study drug treatment interruption based on clinically significant adverse drug reaction (i.e. bleeding events).

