7.3 Dose modification due to treatment related AE – clinically relevant bleeding

Clinically relevant bleeding is the main potential risk based on the pharmacological action of ALX-0081. It is defined as moderate to severe (including life-threatening) bleeding requiring urgent medical and/or surgical intervention. In case of clinically relevant bleeding, appropriate treatment for bleeding according to standard practice should be initiated and treatment with study drug must be interrupted. In addition, plasma levels of vWF:Ag and FVIII chromogene should be determined. If FVIII < 10%, assess for anti-FVIII antibodies and if presence is confirmed, permanently discontinue study drug. If either or both vWF and FVIII are at clinically significant low levels, administration of vWF and FVIII through commercially available combination preparations, such as Haemate-P or equivalent antihemophilic factor/vWF complex should be initiated and continued until the bleeding stops. Study drug should only be restarted when the bleeding has stopped and vWF > 50% and FVIII level is within normal range. The PE treatment, if applicable, should continue as clinically indicated.

Dosage, method of administration and duration of treatment are summarised in Table 8.

Table 8: Dosage, method of administration and treatment duration.

First study drug administration is 10 mg as an i.v. bolus, administered by a push injection, 15 minutes to 6 hours prior to initiation of PE on study.* This first PE on study is followed by subcutaneous (s.c.) administration of 10 mg study drug.

* As discussed in section 4.2, one PE session prior to randomisation is allowed. In such case, the second PE session will be the first PE on study.

S.c. study drug administration during treatment phase with PE	
Frequency of PE	Treatment administration - daily
1 PE/day	Administer 10 mg study drug within 30 min after end of PE
2 PEs/day	
 For subjects receiving anti-vWF Nanobody: administer 10 mg study drug within 30 min after each PE For subjects receiving placebo, maintain a once daily dosing regimen
Tapering (< 1 PE/day)	Daily administration of 10 mg study drug. On days with PE: within 30 min after end of PE; on days without PE at 24 h (\pm 1 h) after previous administration

S.c. study drug administration (in hospital and at home) for **30 days after the very last PE** (including tapering and PE given for exacerbations)*: 10 mg study drug once daily.

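### SAP 6.4.5 counts abnormal laboratory results without separating low from high and plans no per-subject lowest value or threshold count for vWF:Ag or FVIII, so the vWF:Ag count can favour ALX-0081 while more of its subjects are below range

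*SAP*

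**What the plan says.** SAP 6.4.5 plans three kinds of laboratory table.

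- **Abnormality count.** "The number and percentage of subjects with abnormal laboratory results will be presented by treatment and visit for all tests". Abnormal is not defined and no direction is given, although the same section has each out-of-range value flagged high or low on the laboratory sheet.
- **Shift tables.** These present the "shift in result (low, normal, high) from baseline to Day 1 after last PE and from baseline to last day of treatment phase". Both points are relative to the subject's own course.
- **Continuous summaries.** Actual value, change and percentage change at all available visits. Under SAP 6.1.1 these include the minimum and maximum, and all data are listed.

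SAP 6.5.2 adds subject profile plots and summary statistics for central-laboratory vWF and FVIII. Only RICO gets a threshold count there (subjects and days below or at least 20%).

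On the expected direction, Protocol 2.6 notes that "vWF plasma concentrations in patients with signs and symptoms of TTP can be considerably higher than in healthy volunteers". For subcutaneous dosing in healthy subjects, Protocol 2.5.1 reports: "The average decrease of vWF levels ranged from approximately 50% decrease in low dose groups to 70% decrease". The same section gives a sustained FVIII fall of about 50% on multiple dosing. It also says that in repeat-dose monkey studies "anti-FVIII antibodies (AFA) were detected in 4 male animals with no associated clinical signs". Protocol 7.3, on clinically relevant bleeding, contains: "If FVIII < 10%, assess for anti-FVIII antibodies and if presence is confirmed, permanently discontinue study drug".

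**The concern.** Protocol 7.3 and SAP 6.4.6 name clinically relevant bleeding as the main potential risk, and the fall in vWF and FVIII is the laboratory effect closest to it. For vWF:Ag, high and low values mean different things here. A high value is expected from the disease, and a low value is the expected drug effect. A table that adds them together can show fewer abnormal results on ALX-0081 because the drug moves high values into range, while more of its subjects fall below range.

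The shift tables do separate direction, but only at two post-baseline points, so a transient low between them is not tabulated by category. How many subjects per arm were ever low on treatment is a natural safety question, and no planned table answers it for either analyte.

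**Working it through.** The plan states no figure on this point, so there is nothing to reproduce. Three checks follow.

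**1. Can the undivided vWF:Ag count point the other way?**

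Inputs from the documents: 110 adults randomised 1:1, so 110/2 = 55 per arm (SAP 6.1.4); a vWF fall of 50–70% (Protocol 2.5.1); raised vWF in TTP, with the dose rationale considering levels 1 to 3 fold above those studied before (Protocol 2.6). Assumptions: normal range 50–150%, lognormal values, CV 30–50%, median off drug 100–300%, no change on placebo, and no separate allowance for plasma exchange.

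With s = √ln(1 + CV²), P(low) = Φ[(ln 50 − ln m)/s] and P(high) = 1 − Φ[(ln 150 − ln m)/s], where m is the arm's median. At CV 40%, s = √ln 1.16 = 0.385.

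Worked case, median 200% off drug, 60% fall:
- Placebo, m = 200: P(high) = 1 − Φ(−0.75) = 0.772, and 55 × 0.772 = 42.5. Low is 0.0.
- ALX-0081, m = 200 × 0.4 = 80: P(low) = Φ(−1.22) = 0.111, giving 6.1. P(high) = 1 − Φ(1.63) = 0.051, giving 2.8. The total is 8.9.

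Expected subjects of 55 at one visit, CV 40%, shown as low / high / either:

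| Median off drug | Placebo | 50% fall | 60% fall | 70% fall |
|---|---|---|---|---|
| 100% | 2.0 / 8.0 / 10.0 | 27.5 / 0.1 / 27.6 | 39.5 / 0.0 / 39.5 | 49.9 / 0.0 / 49.9 |
| 150% | 0.1 / 27.5 / 27.6 | 8.0 / 2.0 / 10.0 | 17.5 / 0.5 / 18.0 | 33.4 / 0.0 / 33.5 |
| 200% | 0.0 / 42.5 / 42.5 | 2.0 / 8.0 / 10.0 | 6.1 / 2.8 / 8.9 | 17.5 / 0.5 / 18.0 |
| 300% | 0.0 / 53.0 / 53.0 | 0.1 / 27.5 / 27.6 | 0.6 / 15.5 / 16.1 | 3.5 / 5.1 / 8.6 |

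- At medians of 200–300% the undivided count is lower on ALX-0081 for every fall and every CV from 30% to 50%.
- At 150% it is lower for falls of 50% and 60% and higher for 70%.
- At 100% it is higher throughout, so nothing is masked.
- At 300% few subjects are low, so little is hidden. The effect matters most between about 150% and 200%.

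**2. How much of the series do the shift tables use?**

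Protocol 8.1.2 schedules local coagulation samples three days a week during daily PE, once on the day after, then weekly. Over d days of daily PE plus about four weekly samples, the number is about round(3d/7) + 1 + 4. For d = 4, 6 and 16 (illustrative durations) this gives 7, 8 and 12 samples. Two shift points are then 2/7 = 29%, 2/8 = 25% and 2/12 = 17% of them. Central-laboratory samples come on top.

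**3. What do the documents do elsewhere?**

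- Protocol Table 6 counts Phase I subjects with vWF < 50% and FVIII < 50%. Summing the active rows, vWF is (3+1+3+0+3) + (5+5) = 20 of 27 and FVIII is (0+1+3+2+3) + (3+5) = 17 of 27. Placebo is 0 of 9 for both.
- SAP 6.5.2 counts subjects and days by RICO threshold.
- SAP 6.4.4 tabulates ECG shifts from baseline to all subsequent readings.

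**The case against.** The strongest reply is that low values are widely displayed already. A reader might infer that they appear only in the shift tables. That is not so: per-visit minima, change summaries, profile plots and listings all show them. A reader might also infer that a single near-zero FVIII would vanish because it hardly moves a mean. It would appear as the arm's minimum at that visit.

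A reader might further infer that a low nadir is never counted. Protocol 8.3.7 makes every out-of-range coagulation value an AE, and SAP 6.4.1 counts AEs by preferred term and arm. However, Protocol 8.3.1 and SAP 6.4.5 make only clinically significant values AEs, and the passages conflict. Protocol 2.4.2 shows how little a judgement-based route may capture: 17 of 27 active subjects had FVIII < 50%, yet no FVIII decrease was recorded as clinically significant or as an AE.

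Other points on that side stand.
- Both shift points fall during once-daily dosing, so a sustained fall should show in the low column.
- Protocol 10.3 promises descriptive summaries and shift tables, which the SAP delivers. Table 6 belongs to an earlier study, so leaving out its thresholds breaks no commitment.
- The FVIII < 10% level applies only within the bleeding pathway; the documents attach no action to it otherwise.
- The table shells and the DSMB's own SAP are not available, and either may show direction.

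What remains is that a minimum is one subject's value at one visit, and plots and listings are not counts by arm.

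**Conclusion.** The point holds as a gap in tabulation. The by-visit count is undefined and undirected, category shifts are limited to two points, and vWF:Ag and FVIII have no per-subject lowest value or threshold count.

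The possible misdirection is large for vWF:Ag under plausible assumptions (42.5 against 8.9 out of range, with 0.0 against 6.1 low, at a median of 200% and a 60% fall). It is still conditional. It rests on an assumed normal range, spread and off-drug level, and it reverses at a median of 100%. It should not be extended to FVIII, because the documents give no raised FVIII baseline in TTP. For FVIII the gap is only the missing count of subjects ever low.

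Nor do the documents support a claim that the safety outputs as a whole would hide a coagulation effect. These are descriptive tables without formal testing, so no test result is affected. The change is still worth making, because it concerns the drug's main named risk and costs little.

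**What to change.** In SAP 6.4.5:

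1. Define abnormal as outside the normal range, and report below-range and above-range counts separately by treatment and visit, using the existing high/low flags.
2. Keep the two planned shifts and add one from baseline to the worst on-treatment value. For vWF:Ag and FVIII the worst value is the lowest; state the direction for any other parameter included.
3. For vWF:Ag and FVIII, local and central shown separately, summarise by arm each subject's lowest value from first to last dose. Give the number and percentage ever < 50% (both analytes, as in Protocol Table 6) and ever < 10% (FVIII, a level named in Protocol 7.3). Use subjects with at least one on-treatment sample as the denominator, and print the number of samples per subject, because longer daily PE means more chances to record a low value.

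These are descriptive counts only, and no clinical rule changes. Separately, Protocol 8.3.7 must be reconciled with Protocol 8.3.1 and SAP 6.4.5 on which coagulation values are recorded as AEs, so that the AE tables can be interpreted.

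The cost is SAP wording and a few table rows from data already collected. The downside is a slightly longer laboratory output and counts that may look less favourable to ALX-0081.
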